5.4. Handling of Dropouts or Missing Data

Rules for handling dropouts or missing data are listed by type of analysis alphabetically. Unless otherwise specified, observed data will be used and missing data will not be imputed or carried forward.

In the event that the date of progression is reported only to the nearest month, the date will be imputed for analysis (assumed to have occurred on the 15th day of the reported month).

General rules for imputing dates related to AE or concomitant therapy:

- Onset date of an AE or start date of a concomitant therapy:
 - If only the day is missing, the date will be set to:
 - First day of the month that the event occurred, if the onset yyyy-mm is after the yyyy-mm of first study treatment.
 - The day of the first study treatment, if the onset yyyy-mm is the same as yyyy-mm of the first study treatment.
 - If month is missing, the month should be set to July.
- Resolution date of an AE or end date of a concomitant therapy:
 - If only the day is missing, the date will be set to the last day of the month of the occurrence, or to the date of death if the patient died in the same month.
 - If month is missing, the month should be set to July.

If an onset date for an AE is missing, then the AE will be considered treatment emergent with unknown onset date. For additional therapies, if the start date is missing then the therapy will be assumed concomitant.

General rule for imputing other dates: If a date variable is needed for an analysis, use the following general rule to impute incomplete date:

- If only the day is missing, then assign Day 15 to the day.
- If month is missing, the month should be set to July.

However, after imputation, check if the imputed date is logically consistent with other relevant date variable(s) and make appropriate correction if necessary. For example, if a visit start date was 16 May 2008 and a tumor assessment date was xx May 2008 (missing day) but it was known that it occurred on or after that visit, then after imputation, the tumor assessment date became 16 May 2008. In this case, the imputed tumor assessment date should be compared to the visit start date and then corrected to be the later of the 15th day of the month and the visit start date.

Safety analysis: The following rule for missing data processing will apply for safety analysis:

- Missing classifications concerning study medication relationship will be considered as related to study medication (both components).
- If the AE onset date is missing or partial, the date will be compared as far as possible with the date of first dose of study medication when determining whether or not the AE is present at baseline. In this case, the AE will be assumed to be treatment emergent, unless there is clear evidence (through comparison of partial dates) to suggest that the AE started prior to the first dose of study medication.

5.5. Study Patients

5.5.1. Analysis Population

Table JGDM.5.2 lists analysis population definitions and associated data type for analysis.

Table JGDM.5.2. Analysis Populations

Population	Definition	Analysis Type / Variable	Note
All Entered Patients	All patients who signed Inform Consent		
Safety Population	All enrolled patients who receive any quantity of investigational product (IP), regardless of their eligibility for the study, will be included in the safety analysis.	Baseline characteristics, concomitant medication, efficacy analyses, Safety, e.g. dosing/exposure, AE and resource utilization.	Safety evaluation will be performed based on the assigned therapy. Select analyses will be conducted by cycle 1 versus cycle 2 onward.
Efficacy Population	The efficacy analysis will be performed on the intent-to-treat (ITT) population, which includes all enrolled patients that have received any quantity of investigational product (IP), regardless of their eligibility for the study.	The ITT population will be included in overall patient listings, in summary tables of patient demographics and disease characteristics, in the list of treatment discontinuation after enrollment, and in the analysis of efficacy.	
Biomarkers Evaluable 1 Population (BE1)	
The biomarker evaluable 1 (BE1) population will include all ITT patients with evaluable samples at both baseline and post-olaratumab monotherapy.
 
If the patient is noncompliant during olaratumab monotherapy (Cycle 1) and does not undergo the post-olaratumab monotherapy biopsy or the C1D1 pre-dose and C2D1 predose whole blood sample collection due to reasons other than drug-related toxicity, he or she will be considered nonevaluable
	The BE1 population will be used in the biomarker analyses for the primary objective and exploratory objectives.	
Biomarkers Evaluable 2 Population (BE2)	The biomarker evaluable 2 (BE2) population will include all ITT population with evaluable samples at both baseline and post-combination (olaratumab plus doxorubicin) therapy. If the	The BE2 population will be used in the biomarker analyses for the exploratory objectives.	

	
patient is noncompliant during olaratumab monotherapy (Cycle 1) and does not undergo the post-olaratumab monotherapy biopsy or the C1D1 pre-dose and C2D1 predose whole blood sample collection due to reasons other than drug-related toxicity, he or she will be considered nonevaluable
		
--	---	--	--

Abbreviations: AE = adverse event; BE = Biomarker Evaluable; IP = Investigator Product; ITT = Intent-to-Treat.

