10.5. Biomarker Analyses

Primary analysis:

All patients in the BE1 population will be evaluated for:

- CTC enumeration in whole blood
- PDGFR α , PDGFR β , and canonical ligand (*PDGF-A, B, C, and D*) expression in tumor tissue.

The percent change from baseline for post-olatumab monotherapy in biomarker expressions will be provided for each patient and summarized for all qualified patients. Summary of number and frequency of patients with at least 30% reduction in change from baseline PDGFR α expression will also be provided. For patients with an observed value of 0 for baseline expression or both baseline and post-olatumab monotherapy expressions, a value of 0.1 will be used.

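### SAP Table JGDM.5.2 puts one Cycle 1 biopsy-or-blood exclusion on both BE1 and BE2, so valid pairs from noncompliant patients can be dropped, in BE2 over samples it never uses

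*SAP*

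**What the plan says.** SAP 5.5.1, Table JGDM.5.2, opens the BE1 row without naming a sample type: "The biomarker evaluable 1 (BE1) population will include all ITT patients with evaluable samples at both baseline and post-olaratumab monotherapy". A second sentence then covers a patient who is "noncompliant during olaratumab monotherapy (Cycle 1) and does not undergo the post-olaratumab monotherapy biopsy". It adds the blood draws as an alternative trigger and exempts drug-related toxicity: "biopsy or the C1D1 pre-dose and C2D1 predose whole blood sample collection due to reasons other than drug-related toxicity". It ends "he or she will be considered nonevaluable", with no limit on scope.

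The BE2 row is defined by a different comparison (it "will include all ITT population with evaluable samples at both baseline and post-combination" therapy), yet repeats that second sentence in full.

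On use, the table says "The BE1 population will be used in the biomarker analyses for the primary objective and exploratory objectives" and "The BE2 population will be used in the biomarker analyses for the exploratory objectives". Protocol 10.5 sends both primary markers, CTC counts in blood and receptor and ligand expression in tissue, through the one set: "All patients in the BE1 population will be evaluated for" each of them. Neither document defines an evaluable set for a single marker.

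**The concern.** The two primary endpoints come from different specimens, and each needs only its own before-and-after pair. Protocol 8.2.3.1 describes the CTC analysis in terms of blood alone, and protocol 8.2.3.2 describes the expression analysis in terms of tissue alone. A single patient-level flag triggered by either specimen can therefore remove a complete pair of the other. That sits badly with SAP 5.4, which plans to use the data observed.

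In BE2 the mismatch is plainer. The exclusion turns partly on post-monotherapy samples, and these play no part in a comparison of baseline with post-combination. BE2 tissue is already limited because the third biopsy and resection tissue are optional, so pairs there are worth keeping.

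At stake are usable pairs for a primary marker and for the exploratory set. The resulting CTC set would also be selected partly on who underwent the second biopsy.

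**Working it through.** **1. The plan's own figure.** Inputs are 17 hits in 35 evaluable patients and a 95% level (protocol 10.1.1, SAP 5.1). The exact Clopper-Pearson limits are the 2.5% quantile of Beta(17, 19) and the 97.5% quantile of Beta(18, 18). They give 31.4% and 66.0%, which match the stated 31% and 66%.

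**2. The rule as each place states it.**

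| Place | Samples that trigger it | Noncompliance needed | Toxicity exempt | Scope |
|---|---|---|---|---|
| Protocol 7.6.1 | second biopsy, or C1D1 and C2D1 blood | yes | yes | primary objective |
| Protocol 10.1.1 | either biopsy, or C1D1 and C2D1 blood | yes | no | not stated |
| SAP 5.1 | either biopsy, or C2D1 blood | yes | no | not stated |
| SAP Table JGDM.5.2, BE1 | as protocol 7.6.1 | yes | yes | not stated |
| SAP Table JGDM.5.2, BE2 | as protocol 7.6.1 | yes | yes | not stated |
| Protocol 10.1.2, BE1 and BE2 | none | – | – | – |

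The BE2 exclusion exists only in the SAP table. The table also drops the limit to the primary objective that protocol 7.6.1 carries. SAP 5.1 omits C1D1 from its rule although its own list of required samples, one paragraph earlier, includes it.

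**3. The table applied to four patients.** I take a missing C1D1 or C2D1 draw to break the blood pair; the sentence does not say whether one missed draw is enough.

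- *A: noncompliant, both biopsies done, C2D1 blood missed, valid post-combination samples.* The tissue pair is complete but A leaves BE1. A also leaves BE2, although C2D1 blood is neither its baseline nor its post-combination sample.
- *B: noncompliant, C1D1 and C2D1 blood drawn, second biopsy refused.* The CTC pair is complete but B leaves BE1. Protocol 6.2 defines the combination period as starting once the post-Cycle 1 biopsy has been taken, so as written B would have no post-combination sample. BE2 losses therefore come mainly from patients like A.
- *C: second biopsy missed because of drug toxicity.* The exclusion sentence does not apply.
- *D: second biopsy taken but inadequate.* It was undergone, so the sentence does not apply.

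For C and D only the opening BE1 sentence governs, and it can be read marker by marker. B, C and D all lack a usable tissue pair, yet only B is expressly removed from the CTC analysis.

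**4. Size.** The documents give no missing rate. Let t and b be the assumed shares of treated patients whose tissue or blood miss triggers the rule, taken as independent. Per N treated, the joint rule keeps N(1−t)(1−b). Marker-specific sets keep N(1−t) tissue pairs and N(1−b) CTC pairs. With N = 35 and t = b:

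| t = b | Pairs per marker | Kept jointly | Valid pairs unused, each marker |
|---|---|---|---|
| 5% | 35 × 0.95 = 33.25 | 35 × 0.95² = 31.6 | 1.7 |
| 10% | 35 × 0.90 = 31.5 | 35 × 0.90² = 28.4 | about 3 |
| 20% | 35 × 0.80 = 28.0 | 35 × 0.80² = 22.4 | 5.6 |

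Independence probably overstates the loss. A noncompliant patient is likely to miss both specimens, and if the misses coincided completely no valid pair would be lost.

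**The case against.** The joint set is a deliberate design choice. Protocol 7.6.1, protocol 10.1.1 and SAP 5.1 all describe the 35 patients as having both biopsies and both blood draws. Protocol 8.2.3.3 plans associations between tissue markers, CTCs and PET, and the tissue-CTC part needs patients with both specimens. The study is descriptive, and the SAP's Revision History says the evaluable population was clarified to follow protocol amendment (c), so the BE2 sentence may be a carry-over. Exploratory biomarker work may also get its own plan (SAP 5.9). This justifies keeping a joint set for replacement and for associations. It does not justify discarding a complete pair from a single-marker summary, and nothing elsewhere corrects the BE2 row.

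Three stronger readings are tempting, and the documents do not support them.

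- *Any missed sample makes a patient nonevaluable.* The sentence requires noncompliance in Cycle 1 and exempts drug-related toxicity.
- *CTC precision suffers by a known amount.* A reader might set f to the share without a second biopsy and compute 1/√(1−f), giving 1.05, 1.12 and 1.20 at 10%, 20% and 30%. At 20% the same reader would find 35/0.8 ≈ 44 treated and about 9 CTC pairs unused. These are at best upper bounds under assumed rates: they treat every missed biopsy as a trigger and every such patient as having both blood samples. No CTC standard error or interval is a planned output.
- *The 31% to 66% interval is at risk.* Nonevaluable patients may be replaced, and protocol 10.1 ties the first database lock to all 35 evaluable patients. At n = 35 the interval stands.

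That the status reaches every biomarker analysis is also an inference. It rests on the unqualified wording and on BE1 and BE2 being the only biomarker sets.

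**Conclusion.** The concern holds for patients noncompliant in Cycle 1 whose sample was missed for some cause other than drug toxicity. The BE2 wording is an error: it excludes patients over samples outside its own comparison and departs from protocol 7.6.1 and 10.1.2. In BE1 the literal rule can remove a valid CTC or tissue pair, and marker-specific sets would avoid that.

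The number affected is unknown and probably small, because the trigger is narrow and a patient without the second biopsy should not, as written, reach combination therapy. The tabulated 1.7 to 5.6 unused pairs per marker per 35 treated rest on assumed, independent rates of 5% to 20%. The plan's stated precision is not affected. This is a wording correction worth making before the populations are programmed.

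**What to change.** 1. Delete the Cycle 1 noncompliance sentence from the BE2 row, leaving baseline and post-combination samples as the only criterion, as in protocol 10.1.2.
2. In BE1, analyse each primary marker on all patients with that marker's own evaluable pair. BE1-CTC would need C1D1 and C2D1 counts; BE1-tissue would need pre- and post-monotherapy biopsies.
3. Keep the joint biopsy-and-blood definition for the replacement rule and for tissue-CTC association analyses, and restore the limit to the primary objective where the word nonevaluable is used.
4. State the rule once and align SAP 5.1, Table JGDM.5.2 and protocol 7.6.1 and 10.1.1 on C1D1, the pre-treatment biopsy and the toxicity exception.

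The cost is wording only, with no new samples and no change to the target of 35. The one drawback is that denominators will differ between endpoints, so each biomarker table should show its own n.

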5.5.2. Patient Disposition

A detailed description of patient disposition will include:

- Summary of the number of patients who entered into the study, and who received at least one dose of study treatment, by site, assigned treatment and overall.
- The summary of the number (and percent) of patients with the primary reasons for discontinuation from study treatment and patients still receiving treatment by assigned treatment and overall. The discontinuation reasons collected in CRF (eg. AE, PD, death, and etc) will be presented.
- Listing of patient discontinuation.

5.5.3. Demographic and Baseline Characteristics

The following patient demographic and other baseline characteristics will be summarized:

- patient demographics: age (years) and age group, gender, race (White, Black, Asian, All Other), ethnicity, height (cm), weight (kg), and BSA (m2), ECOG performance status
- baseline disease characteristics:
 - at study entry only: current disease stage, grade, duration of disease (months), lung disease (yes, no)
- prior cancer therapies: type of therapy (surgery, radiotherapy, systemic therapy), type of prior surgery, type of prior radiotherapy, and type of prior systemic therapy
- Medical history by MedDRA PT, presented in decreasing frequency

Note: Subjects reporting more than 1 condition/diagnosis within a PT will be counted only once for that PT.

Patient listings of demographic data and baseline characteristics will be provided. Patient listings of prior cancer therapies (surgery, radiotherapy, and systemic therapy) will also be provided.

Other patient characteristics will be summarized as deemed appropriate.

5.6. Important Protocol Deviations

Protocol deviations will be identified in Protocol Deviation Plan. Important protocol deviations (e.g. not meeting inclusion/exclusion criteria, noncompliance with protocol procedures, dosing errors, use of prohibited medication, continuing after meeting withdrawal criteria) will be listed by treatment group and by category of deviations.

5.7. Concomitant Medications

The following concomitant medications used during study treatment period or up to the 30-day (± 7 days) postdiscontinuation follow-up period will be summarized by numbers and percentages by dose cohort, presented in decreasing frequency of the World Health Organisation drug term:

- all concomitant medications
- premedication for study drug

Patient listing of all concomitant therapies and premedications will be provided.

5.8. Treatment Compliance

The number of dose omissions, reductions, and delays, and the number of cycles received will be summarized by cohort.

A by-patient listing of treatment compliance data will be provided.

5.9. Biomarker Analyses

The primary endpoints of the study are

- CTC enumeration changes pre- and post-olatumab monotherapy in whole blood
- PDGFR α and PDGFR β and canonical ligands (PDGF-A, B, C, and D) expression changes pre- and post-olatumab monotherapy in tumor tissue

The percent change from baseline for post-olatumab monotherapy in biomarker expressions will be provided for each patient and summarized for all qualified patients in the BE1 population. For patients with an observed value of 0 for baseline expression or both baseline and post-olatumab monotherapy expressions, a value of 0.1 will be used. In particular, summary of number and frequency of patients with at least 30% reduction in change from baseline PDGFR α expression will be provided.

Exploratory biomarker analyses may be described in a separate biomarker statistical analysis plan, if deemed necessary.

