8.2.3.1. Blood Samples

Whole blood samples are required for all patients in order to participate in this study for biomarker research:

- newly obtained peripheral whole blood specimens will be collected specifically to enumerate CTCs. These specimens will be collected at C1D1 (predose), C1D8 (predose), C2D1 (predose), C2D8 (predose), C3D1 (predose), and at the end of the patient's study treatment or at the time of surgical resection. Refer to [Attachment 4](#) for details.
- blood (ethylenediaminetetraacetic [EDTA] plasma, serum) samples for nonpharmacogenetic biomarker research will be collected. Refer to [Attachment 4](#) for details.

Newly obtained peripheral whole blood specimens are to be collected specifically to enumerate CTCs. Sequentially collected blood specimens will be used for CTC detection and enumeration. The primary analysis of these samples will be focused on the relationship between pre-olatumab monotherapy and on-treatment (post-olatumab monotherapy treatment) CTC counts. These samples may be used for other exploratory analyses and further molecular characterization.

Additional blood (EDTA plasma, serum) samples for nonpharmacogenetic biomarker research will be collected. These samples will be examined for biomarkers related to STS, immune cells/immune and tumor microenvironment functioning within the disease state and/or cancer-related conditions, variable response to olatumab and/or doxorubicin, and the MOA of olatumab or doxorubicin. Potential pharmacodynamics and/or circulating markers may include, but are not limited to, PDGF receptors, canonical ligands (*PDGF-A, B, C, and D*), and downstream signaling pathways. Biomarker assays may be performed on these samples to evaluate systemic immune modulation and changes in immune cell infiltration, activation, modulation, microenvironment, and changes in stromal and tumor biology in response to study treatment.

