	10			48 hours ± 3 hours	X				
	12			96 hours ± 3 hours	X				
18			240 hours ± 3 hours	X					
3	1			Prior to olaratumab infusion ^f	X	X	X		
			X						
		X							
	8			Within 5 min post doxorubicin infusion	X				
				Prior to olaratumab infusion ^f	X				
			X						
			Within 5 min post olaratumab infusion	X					
5, 7	1			Prior to olaratumab infusion ^f	X	X			
30-day follow-up				Anytime	X	X	X ^e	X	X

Abbreviations: CTC = circulating tumor cells; IG = immunogenicity; min = minutes; olara = olaratumab; PK = pharmacokinetic.

- a Time 0 is defined as end of infusion.
- b Samples of approximately 3 mL of whole blood will be drawn into tubes. For the olaratumab samples, olaratumab serum PK measurements will be performed.
- c Samples of approximately 4 mL will be collected.
- d In addition to the scheduled immunogenicity sampling, in the event of an infusion-related reaction, samples are to be collected as close to the onset of the event as possible, at the resolution of the event, and 30 days following the event.
- e At end of the patient's study treatment.
- f Pretreatment PK samples may be collected up to 60 minutes prior to the olaratumab infusion and must be collected prior to administering any premedication.

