5.2. General Considerations

Statistical analysis of this study will be the responsibility of Eli Lilly and Company (Lilly). The analyses for this study will be descriptive, except for possible exploratory analysis as deemed

appropriate. Data analyses will be provided by cycle (cycle 1 versus cycle 2 onward) for specified analyses and for all study patients combined wherever appropriate. For continuous variables, summary statistics will include number of patients, mean, median, standard deviation, minimum, and maximum. Categorical endpoints will be summarized using number of patients, frequency, and percentages. Unless otherwise specified, missing data will not be imputed.

The interpretation of the study results will be the responsibility of the investigator with the Lilly Clinical Research Physician (CRP)/Clinical Research Scientist (CRS), pharmacokineticist, and statistician. The CRP or CRS and statistician will also be responsible for the appropriate conduct of an internal review for both the final study report and any study-related material to be authorized by Lilly for publication.

Exploratory analyses of the data not described below will be conducted as deemed appropriate.

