5.3.1. Circulating Tumor Cells (CTC) enumeration in blood

For all samples collected for each patient, circulating tumor cells identified by a combination of morphology and/or diagnostic staining characteristics will be enumerated as a simple count of circulating tumor cells per milliliter of peripheral blood.

5.3.2. *PDGFR α and PDGFR β protein expression in tumor tissue*

PDGFR α and PDGFR β protein expression will be assessed by immunohistochemical staining interpreted by a pathologist experienced in interpreting these assays. Separate assays will be used for each receptor. Results of both assays will be reported as qualitatively positive or negative based on analytically validated criteria for interpretation of each assay's protein expression score.

5.3.3. *PDGF-A, B, C, and D canonical ligand expression in tumor tissue*

PDGF-A, B, C and D ligand expression will be assayed by real-time RT-PCR with relative quantification to housekeeping genes MRPL19, SF3A1 and PPIA. Normalized relative expression data will be reported using the Ct value of the gene of interest (GOI) and average Ct of the reference genes for that sample (RG) transformed with the following formula: $2^{-(20-GOI+RG)/1000}$. Additional approaches for normalizing and reporting relative gene expressions may be explored as deemed appropriate.

5.3.4. *Safety Variables*

Safety measures that will be used in the study include adverse events (AEs), DLT, clinical laboratory test results, vital signs, electrocardiograms (ECGs) and ECHO/MUGA scanning.

Adverse event-related variables are listed below:

- **Adverse event (AE)** is defined as any untoward medical occurrence in a patient administered a pharmaceutical product, without regard to the possibility of a causal relationship.
- **AEs of special interest (AESIs)**

AESI for olaratumab:

- Infusion-related reactions (IRRs)

AESI for combination of olaratumab and doxorubicin:

- Cardiac arrhythmias and cardiac dysfunction

Notes: Categories of AESI may be modified as the understanding of the safety of the investigational drug increases. The final list of categories will be maintained at both compound and study level and reported in the clinical study report (CSR).

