5.14. Interim Analysis

With limited prior experience with the performance of the biomarker assays (i.e, QC issues, dynamic range, data variability), an interim analysis will be done to evaluate the biomarker data once approximately half of the evaluable patients complete the second tumor tissue biopsy and C2D1 whole blood draw. The purpose of this interim analysis is to review the biomarker data in order to identify technical issues that may potentially impact the study's ability to meet its key objectives. If this interim look at the biomarker data warrants any changes in the study conduct, it will be implemented in an appropriate manner (that is, protocol amendment). At this interim analysis, a review of the safety data will also be conducted.

This would be in addition to the safety data review that will be conducted after 5 patients have completed 2 cycles of treatment.

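### A unitless 0.1 stands in for a zero baseline before raw percent change is taken; if this covers CTC, the mean change depends on an assayed volume the documents do not state

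*SAP*

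**What the plan says.** CTC change before and after olaratumab monotherapy is one of the two primary objectives (Protocol 5.2.1, SAP 4.1). Protocol 8.2.3.1 ties the blood samples to it: "The primary analysis of these samples will be focused on the relationship between" the counts before and after monotherapy. SAP 5.3.1 fixes the unit: cells are "enumerated as a simple count of circulating tumor cells per milliliter of peripheral blood".

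SAP 5.9 takes the percent change from baseline for each patient and summarises it in the BE1 population. It then adds a zero rule: "For patients with an observed value of 0 for baseline expression or both baseline and" post-monotherapy values, 0.1 is substituted. Protocol 10.5 has the same rule ("a value of 0.1 will be used"). A zero that occurs only after treatment is left as zero. Neither document gives the constant a unit, a detection limit or a reason.

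Under SAP 5.2, "summary statistics will include number of patients, mean, median, standard deviation, minimum, and maximum". No lead summary is named.

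Protocol Attachment 4 gives a volume for the pharmacokinetic sample (footnote b: "Samples of approximately 3 mL of whole blood will be drawn into tubes") and for the immunogenicity sample (footnote c: "Samples of approximately 4 mL will be collected"). It gives none for the CTC draw.

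**The concern.** Percent change divides by the baseline. With a zero baseline the divisor becomes the constant, so the constant sets the size of the result. On a per-mL scale, a single cell can be worth more or less than 0.1 depending on how much blood was assayed. The same laboratory finding, no cells before and one after, can then be scored as a large rise, as no change or as a fall.

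At stake is the summary of a primary objective in a single-arm study, where no control group shares the artefact. Percent change is the only measure of CTC change that the SAP defines. Rare cells make zero baselines plausible, and the documents give no expected CTC density that would rule them out.

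**Working it through.** **The plan's own figure.** The only statistical figure in the sample-size section is the 95% CI for a PDGFRα hit rate of 17/35. The exact (Clopper-Pearson) interval is 31.4% to 66.0%, which matches the stated 31% to 66%. It does not involve CTC, and nothing below changes it.

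**One new cell, exact arithmetic.** Inputs: constant 0.1 (SAP 5.9), unit cells per mL (SAP 5.3.1), assayed volume V (not stated, so assumed). A zero baseline becomes 0.1, and one cell after treatment is 1/V. The score is (1/V - 0.1)/0.1 = 10/V - 1.

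| Assumed V (mL) | Score for 0 to 1 cell |
|---|---|
| 1 | +900% |
| 4 | +150% |
| 7.5 | +33% |
| 10 | 0% |
| 20 | -50% |

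The sign changes at 10 mL. Zero at both times scores 0%.

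**One case worked exactly, no true change.** Assume the expected number of cells per sample is gamma distributed with mean 1 and shape 1, and that the two counts are independent Poisson given that mean.
- Half of baselines are zero. Among them the expected post count is 0.5, and one third have at least one cell. Their average score is 10 × 0.5/V - 1/3 = 5/V - 1/3.
- A baseline of k cells (k = 1, 2, ...) has probability 1/2^(k+1) and expected post count (1+k)/2, so its score is 1/(2k) - 1/2. Summed over k this contributes (ln 2)/4 - 0.25 = -0.077.
- Overall mean: 0.5 × (5/V - 1/3) - 0.077 = 2.5/V - 0.243.

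This gives +226% at 1 mL, +38% at 4 mL, +9% at 7.5 mL, +1% at 10 mL and -12% at 20 mL. The distribution of cell counts is identical throughout; only V differs. Dropping the zero baselines gives -0.077/0.5 = -15% at every V, because the patients kept were selected for having a cell at baseline.

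**Simulation over a range.** 4000 trials of 35 patients per scenario; density 0.05 to 10 cells/mL; gamma shape 0.5 and 1; Poisson counts. The zero rule was applied as written.

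| V (mL) | No change: average mean % change | True halving: share of trials with a positive mean |
|---|---|---|
| 1 | +35% to +225% | 39% to 92% |
| 4 | +11% to +45% | at most 33% |
| 7.5 | -3% to +22% | at most 5% |
| 10 | -8% to +17% | at most 1% |
| 20 | -12% to +11% | at most 0.3% |

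The median under no change stays between -3.8% and +0.4%.

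**Which part is to blame.** Using 0.1 for every zero still gives +35% to +226% at 1 mL and +2% to +21% at 20 mL. Dropping zero baselines gives -91% to +13% and -16% to +13%. At 20 mL with 1 to 10 cells/mL, dropping them (+2% to +10%) and the planned rule (+2% to +9%) nearly agree, so there the raw ratio scale is the source. At 1 mL the small divisor dominates: in the exact case, zero baselines contribute 0.5 × (5 - 1/3) = +233 points.

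**The alternative scale.** For ln[(post+c)/(pre+c)] with c = 0.5/V, the geometric mean ratio under no change is 0.995 to 1.005 in all 70 scenarios.

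**The case against.** The rule speaks of *expression*, a word the documents otherwise use for tissue receptors and ligands, while CTC are *enumerated*. On that reading the 0.1 figures do not apply to CTC. This stands as a possible reading. However, Protocol 10.5 lists CTC enumeration directly above the sentence, and if CTC are outside the rule, percent change at a zero CTC baseline has no definition. Either way the text needs a change.

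The study is descriptive and each patient's value is provided. The median is already planned and is nearly unbiased under no change. No test or decision rule uses the CTC mean. SAP 5.3.5 also has CTC assessed before and after treatment, so raw counts could be tabulated. SAP 5.14 opens with "With limited prior experience with the performance of the biomarker assays" in order to schedule an interim look for technical problems such as dynamic range, with changes made by amendment. All of this stands and limits the harm. It does not supply a basis for 0.1, and the median is not named as the lead summary.

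Three stronger readings are tempting. A reader might take +900% and -50% as properties of this trial. They belong to assumed volumes of 1 and 20 mL, and if the assay volume is fixed, every patient shares one V. A reader might blame 0.1 alone, but the comparison above shows that the ratio scale contributes too. A reader might treat the missing volume as proof that it was never set. Attachment 4 gives no volume for plasma or serum either, and a laboratory manual may hold it.

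**Conclusion.** The point holds as a defect worth correcting before CTC data are summarised. It does not invalidate the study. The 10/V - 1 result is exact, given that the rule covers CTC. The size of the distortion in the mean rests on assumed volumes, densities and gamma-Poisson variation. It is severe at 1 mL, moderate at 4 mL, and between -12% and +22% at 7.5 to 20 mL. A mean that points the wrong way under a true halving is mainly a small-volume problem: at 7.5 mL or more it occurs in at most 5% of trials.

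A reader might infer that the primary result as a whole is unreliable. The documents do not support that. The PDGFRα hit-rate target is untouched by the CTC argument, and the listed values and the median remain usable.

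**What to change.** In SAP 5.9:
- State that CTC is covered, and state the assayed volume V.
- For CTC, replace the 0.1 rule and the mean percent change by ln[(post+c)/(pre+c)] for every BE1 patient, with c = half a cell divided by V, fixed in advance.
- Report the geometric mean ratio with its 95% CI, alongside the median and the absolute change in cells per mL.
- Optionally, add total post-treatment cells over total baseline cells. This needs no offset but gives more weight to patients with high counts.

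Carry the same change into Protocol 10.5 at the next amendment.

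The cost is SAP wording and a little programming; no new data are needed. The downside is that the offset pulls the ratio towards 1 when zeros are common. A true halving reads as a 43% to 50% fall at 20 mL with 1 to 10 cells/mL, as 23% to 46% at 1 mL with the same densities, and as only about 3% at 1 mL with 0.05 cells/mL. The absolute change must therefore be shown with the ratio.
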